Background and Rationale: Truvada®, is an oral pill comprised of two anti-retroviral compounds, emtricitabine (FTC) and tenofovir disoproxil fumarate (TDF). Gilead Sciences reported a total of nearly 100,000 individuals in the US starting Truvada for pre-exposure prophylaxis (PrEP) between the years 2012-2016¹, and this number is growing in the US and globally. Adherence to the one pill per day regimen is crucial for its effectiveness in reducing the risk for sexual transmission of human immunodeficiency virus (HIV) infection by 90%, and by 70% from injection drug use². Two landmark safety and effectiveness trials which supported the FDA approval of Truvada for PrEP were the iPrEX trial, which investigated Truvada use in HIV-negative men or transgender women, and the Partners PrEP trial, conducted in serodiscordant couples^{3, 4}. Both showed Truvada reduced risk of HIV infection by 42% (iPrEX) and 72% (Partners PrEP), noting that risk reduction was highly correlated with drug adherence. Another important study supporting PrEP was the TDF2 trial, which showed an HIV risk reduction of 62%⁵. Although other clinical studies did not show efficacy, the results correlating poor drug efficacy with low plasma drug levels did confirm the importance of adherence^{6, 7}. Adherence measured by self-report did not correlate with effectiveness^{6, 7}. Although adherence is key to effectiveness, physicians and other health care providers (HCPs) do not have objective tools to monitor drug adherence and be able to tailor counselling to the actual needs of their patients and clients. The evidence supporting the association between adherence and effectiveness is strong, but only objective assessment of adherence is reliable and correlates with effectiveness. The scientific premise supporting our work is based on this evidence, as well as the absence of a point-of-care objective diagnostic test for drug adherence. The most objective measure of adherence currently available to detect and quantify drug levels in plasma is liquid chromatography tandem mass spectrometry (LC-MS/MS). This method, however, requires a specialized lab and does not qualify as a point-of-care (POC) test. *Therefore, our project is aimed at filling this gap by developing and validating an aptasensor (aptamer-based biosensor), capable of detecting tenofovir (TFV) in various biological fluids at a point-of-care/clinic with a simple-to-use procedure, which will empower HCPs to provide real-time adherence feedback with each prescription renewal.* Ultimately, real-time monitoring of adherence will lead to better counselling, resulting in higher effectiveness and improved success rates for treatment and prevention of HIV infection.

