5.2.1. Primary Objectives

- Compare plasma TFV concentrations measured by the aptasensor with those values quantitated by LC-MS/MS to determine agreement between the two methodologies, sensitivity, specificity, NPV, and PPV
- Determine if the TFV aptasensor can detect differences in the plasma TFV concentrations between high and low adherence dosing regimens and compare the mean difference to the difference calculated from values generated by LC-MS/MS

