5.2.2. Secondary Objectives

- Compare urine TFV concentration measured by the aptasensor with those values quantitated by LC-MS/MS to determine agreement between the two methodologies, sensitivity, specificity, NPV, and PPV
- Determine if the TFV aptasensor can detect differences in the urine concentrations of TFV between high and low adherence dosing regimens and whether these levels correlate with adherence
- Compare vaginal fluid TFV concentrations measured by the aptasensor with preclinical determinations of the range of detectable TFV levels and the aptasensor's limit of detection
- Determine if differences in adherence dosing regimens can be correlated to differences in vaginal fluid TFV levels

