8.2. Visit 2: Baseline Pre-Dose Sample Collection

This visit will be scheduled for the early follicular phase of the menstrual cycle (for cycling women).

- An interval history will be collected.
- Eligibility criteria will be reviewed. If any lab tests reveal that the participant is not eligible, the visit should not proceed and the participant will not continue in the study.
- If indicated by signs or symptoms or history, a directed physical exam and/or urine pregnancy test will be performed. If pregnancy is diagnosed, the participant will be referred as necessary and will be discontinued.

- A vaginal swab for prostate specific antigen (PSA) will be obtained, if the PSA test indicates semen exposure, the visit will be re-scheduled.
- A urine sample will be obtained.
- Vaginal swabs will be obtained
- A blood sample (approximately 2 teaspoons) will be obtained.
- The participant will be randomized to the HA versus LA regimen and will take her first doses of TDF/FTC in the clinic under direct observation and the time of product ingestion will be recorded in the source document. The pill will be ingested after urine, vaginal and blood samples are obtained.
- The participant will confirm her contact information for the medication text reminder.
- Participants will be instructed to refrain from vaginal intercourse for 48 hours prior to visits 3 – 5.

8.3. Visits 3 – 5: 24 hours , 7 days, and 14 days after first dose

Visits 3, 4, and 5 will be scheduled for 24 hours, 7 days, and 14 days after initial dosing at Visit 2, respectively. The time of the visit will assure that it has been at least 24 hours since the participant's last dose of TDF/FTC. At each visit, the following procedures will be performed:

- The study staff will ask the participant if she followed the instructions from the previous visit, and ask about adverse events and concomitant medications.
- If indicated, a directed physical exam, pelvic exam and/or pregnancy test will be performed. If pregnancy is diagnosed, the participant will be referred as necessary and will be discontinued.
- Visits 4 and 5: Study staff will count the number of pills remaining and query the participant on compliance with her assigned dosing regimen.
- A vaginal swab for PSA will be obtained, if the PSA test indicates semen exposure, the participant will be reminded of the restrictions on vaginal intercourse, but the visit will proceed.
- A urine sample will be obtained.
- Vaginal swabs will be obtained

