14.4. Statistical Analysis

Sample size is based on feasibility rather than statistical considerations; thus, analysis will be primarily descriptive. Participant flowchart (e.g. number screened, number with sampling) will be provided. All populations will be defined based on the adherence regimen.

Evaluation of Study Objectives: Study objectives will be evaluated by clinical review of descriptive summaries and graphical displays.

Primary analysis of this study will evaluate the performance of the TFV aptasensor by comparing its measurements of the concentrations of TFV in clinical samples from all women with those values obtained from LC-MS/MS. Correlation and agreement between the TFV levels measured by the aptasensor and LC-MS/MS will be analyzed using scatterplot and linear regression. Continuous variables will be compared between values measured with the aptasensor versus LC-MS/MS using paired comparisons. From this comparison, sensitivity, specificity, NPV, and PPV of the aptasensor will also be determined. Confidence intervals will be calculated to assess precision and margin of error of those

measures. Using the 14 baseline pre-dose samples, each woman will be her own control, and these pre-dose samples will be used for the assessment of specificity and NPV.

The secondary analysis of this study will evaluate whether the aptasensor can detect differences in TFV levels between the two independent cohorts of women taking TDF/FTC at different dosing regimens representing high (7 pills/week) and low adherence (3 pills/week). We will compare the two independent cohorts using an independent samples t test for normally distributed data or a Wilcoxon-Mann-Whitney test for non-parametric data. TFV concentrations from the LA and HA cohorts will be characterized using descriptive statistics (mean, median, interquartile range, minimum and maximum). The values will be compared between the high adherence and low adherence groups as well as comparing the mean difference between groups generated by the aptasensor to that difference generated by LC-MS/ MS. Distributions will be checked to determine normality so as to determine the appropriate statistical test.

Descriptive Statistics: Categorical variables will be summarized by frequencies and percentages. Continuous variables will be summarized by means, standard deviations, medians, quartiles, minima and maxima.

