15.2. Protocol Adherence and Sampling Windows

Visits 3, 4 and 5 should be scheduled so that it has been at least 24 hours since the participant's last dose of study medication. Visit 3 should be conducted 24 hours + 4 hours from the ingestion of the first dose at Visit 2. Visit 4 should be conducted 7 days + 6 hours from the ingestion of the first dose at visit 2. Visit 5 should be conducted 14 days + 6 hours from the ingestion of the first dose at visit 2.

The study site should carefully record the date and time of each collection of blood, urine and CV swabs. The site should carefully record the date and time of each ingestion of medication in the clinic.

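### Agreement with LC-MS/MS is a primary objective, but no planned output commits to reporting how far a single aptasensor reading may lie from the reference

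*Combined protocol and SAP*

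**What the plan says.** Section 5.2.1 has plasma concentrations by aptasensor compared with "values quantitated by LC-MS/MS to determine agreement between the two methodologies, sensitivity, specificity, NPV, and PPV". Section 5.2.2 sets the same aim for urine: "Compare urine TFV concentration measured by the aptasensor with those values quantitated by LC-MS/MS to determine agreement between the two methodologies".

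The method is in Section 14.4 and, in the same words, in the Synopsis under statistical methods: "Correlation and agreement between the TFV levels measured by the aptasensor and LC-MS/MS will be analyzed using scatterplot and linear regression". The next sentence is "Continuous variables will be compared between values measured with the aptasensor versus LC-MS/MS using paired comparisons", with no test, estimate or scale named. The confidence intervals promised there follow the sentence on sensitivity, specificity, NPV and PPV. A general sentence adds that "Continuous variables will be summarized by means, standard deviations, medians, quartiles, minima and maxima", without tying these to sensor-minus-reference differences.

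No section names a difference plot, limits of agreement, a prediction interval, a concordance coefficient or an acceptable difference. Section 14.3 leaves only population definitions to be refined later, so the agreement method is not deferred.

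The Synopsis background says the device is meant to "empower HCPs to provide real-time adherence feedback with each prescription renewal".

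**The concern.** A device that informs feedback to an individual has to be judged on how wrong one reading can be. The planned outputs address other questions.

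- Slope, intercept and mean difference describe average bias.
- r falls as the sensor becomes less precise, but it also moves with the spread of true concentrations.
- Sensitivity, specificity, NPV and PPV measure classification, not quantitative error.

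A regression residual SD, or the SD and range of paired differences, would give the spread. The plan names neither as an agreement result and states no scale. Scale matters: if error grows with concentration, one raw-scale SD is too wide for low readings and too narrow for high ones.

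Two related points are also open. Each woman contributes three post-dose pairs, and the plan does not say whether these are pooled or modelled within woman. Nor does it say how a reading below either method's limit enters the pairs. Section 14.2 rules out imputation of missing values, which touches this but does not settle it.

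**Working it through.** The plan gives no agreement figure, assay error or between-woman SD, so there is no stated number to reproduce.

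**1. Pairs available.** Section 7.3.2 aims for about 14 completers, 7 per regimen. Section 8.3 gives the post-dose times: "Visits 3, 4, and 5 will be scheduled for 24 hours, 7 days, and 14 days after initial dosing at Visit 2". That is 14 × 3 = 42 post-dose pairs. Pre-dose samples, assumed to hold no drug, add nothing on quantitative error.

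**2. Average bias against single-reading error.** In units of the SD of the differences, the 95% CI half-width for the mean is t(0.975, n−1)/√n. A single reading ranges ±1.96 around the bias.

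| n | CI half-width of mean | Single reading | Ratio |
|---|---|---|---|
| 14 (one pair per woman) | 0.577 | 1.96 | 3.4 |
| 42 (treated as independent) | 0.312 | 1.96 | 6.3 |

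A tight interval for the mean difference therefore says little about one reading.

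**3. Two sensors under the planned analysis.** All inputs are assumed: half-life 17 h, first-order decay, between-woman log SD 0.4, the example schedules in Tables 6 and 7, LC-MS/MS taken as true, and independent proportional sensor errors with no average bias. Regression, r and the paired test are on untransformed concentrations. The single-reading range is exp(±1.96 × SD) around the sensor's median ratio.

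| | Error log SD 0.2 | Error log SD 0.5 |
|---|---|---|
| Single-reading range | 0.68 to 1.48 | 0.38 to 2.66 |
| Mean slope | 1.00 | 1.00 |
| Slope, 95% of trials | 0.86 to 1.16 | 0.66 to 1.47 |
| Paired test non-significant | about 95% | about 94% |
| Mean r (95% of trials) | 0.95 (0.91 to 0.98) | 0.78 (0.62 to 0.90) |

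With the concentration range fixed, r does tell the sensors apart.

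**4. Dependence of r on range.** Section 15.2 sets only a minimum gap: "Visits 3, 4 and 5 should be scheduled so that it has been at least 24 hours since the" most recent dose. Table 7 is labelled an example and implies 72 h before Visits 4 and 5. I varied half-life (12 to 24 h), between-woman SD (0.2 to 0.6) and the low-adherence gap (24, 48 or 72 h). The gaps only vary the concentration range; none is proposed. Mean r was 0.75 to 0.96 for the SD 0.2 sensor and 0.41 to 0.82 for the SD 0.5 sensor. A value of 0.75 to 0.82 fits either.

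**5. Scale.** For error SD 0.5 and gaps of 24, 48 and 72 h, raw-scale limits (1.96 × SD of differences) were about ±1.4, 3.1 and 7.2 times the low-adherence Visit 4/5 median. Using 1.96 × the regression residual SD gave 1.3, 3.0 and 7.1. The raw limits from the SD of differences held 96% to 100% of low-adherence Visit 4/5 readings but only 86% to 90% of high-adherence ones. Log-ratio limits held about 95% in each arm.

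**6. Precision with 14 women.** The estimated upper log-ratio limit fell, in 95% of runs, at 1.34 to 1.68 (SD 0.2) and 2.08 to 3.61 (SD 0.5). With a within-woman error correlation (ICC) of 0.7 the ranges were 1.27 to 1.73 and 1.82 to 3.90. The two sensors remain distinguishable.

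**7. Clustering.** If pairs are pooled and errors correlate within woman, the CI for mean bias is too narrow by √(1 + 2 × ICC): √1.6 = 1.26 at 0.3 and √2.4 = 1.55 at 0.7. A pooled 95% CI for the upper limit covered 95%, 91%, 87% and 81% at ICC 0, 0.3, 0.5 and 0.7. An interval built from between- and within-woman components covered 95% to 96% throughout.

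**8. Unquantifiable readings.** With error SD 0.5 and an assumed sensor limit at the low-adherence 72 h median, about 7 of 42 pairs drop out. The mean ratio in the kept pairs is 1.07 overall. In kept low-adherence Visit 4/5 pairs it is 1.37 (limits 0.63 to 2.95), against a truth of 1.00 (0.38 to 2.66).

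**The case against.** The strongest reply is that the plan lacks a commitment, not a workable analysis. Regression yields a residual SD, and the natural variable of a paired comparison is the difference, whose SD and range the general descriptive sentence could cover. A log-log residual SD would separate the two sensors above, at 0.16 to 0.24 against 0.39 to 0.61 in 95% of trials. A scatterplot of at most 42 points shows the scatter directly, and Section 14.4 relies on review of graphical displays. The actual LC-MS/MS range will be observed, so the ambiguity in r is smaller in practice than the grid suggests. The clustering and scale points are conditional, and a 14-woman pilot sized on feasibility need not prove fitness for clinic use.

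Most of this is right, and it limits the severity. The spread can be recovered later from the same data, and no decision rule depends on it. It does not remove the gap. The plan names the methods for a primary objective, and none of them obliges the report to give the spread or to choose a scale. On the raw scale, the residual SD carries the same fault as the SD of differences. Limits of agreement are themselves descriptive, so they suit a pilot.

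**Conclusion.** The concern holds and should be fixed. Agreement is a primary aim, yet the stated analysis can be completed in full without reporting single-reading error. In the assumed case, sensors with ranges of 0.68 to 1.48 and 0.38 to 2.66 had the same mean slope and nearly the same paired-test result. They differed in r, which is not a measure of error size.

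The reading of the text needs no assumptions. The sizes rest on the assumed half-life, between-woman spread, proportional error and dosing gaps. The clustering effect requires both pooling and correlated errors; at ICC 0 there is none. The consequence is a less informative primary result, not a wrong trial decision.

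**What to change.** In Section 14.4 and the Synopsis statistical methods, add wording such as:

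*Agreement will be reported as the mean aptasensor/LC-MS/MS ratio with 95% limits of agreement and confidence intervals, in post-dose plasma samples, from a model for the log ratio with a random woman effect. These results are descriptive.*

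The limits are exp[mean ± 1.96 × √(between-woman variance + within-woman variance)]. Also:

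- First check that error is roughly proportional to concentration. If it is not, give limits by concentration range.
- Keep the scatterplot and regression as supporting displays, and the pre-dose samples for specificity and NPV.
- Report by arm and visit how many samples were quantifiable by both methods, by LC-MS/MS only, by the sensor only, or by neither. State that limits from samples quantifiable by both may be selective at low concentrations.
- Do the same for urine.

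The random-woman model is one reasonable choice. The minimum that closes the gap is limits of agreement, or the SD of paired differences, on a stated scale.

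The cost is wording in two places and modest programming, with no new samples or assays. The limits will be imprecise: at error SD 0.5 a typical 95% CI for the upper limit is 2.1 to 3.8, or 1.9 to 4.5 at ICC 0.7. Intervals may also be wider than pooled ones.

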5.2. Objectives

Compare plasma, urine, and vaginal fluid TFV concentrations measured by the aptasensor with those values quantitated by LC-MS/MS to determine agreement between the two methodologies, sensitivity, specificity, NPV, and PPV.

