5.3. Endpoints

5.3.1. Primary Endpoint

- TFV concentrations in *plasma* at baseline (pre-dose), 24 hours, 7 days and 14 days after dosing

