7.2. Exclusion Criteria

Volunteers must not meet any of the following criteria prior to baseline sampling:

1. Currently pregnant
2. Currently breastfeeding or planning to breastfeed during the course of the study
3. In the last three months, diagnosed with or treated for any STI

4. Positive test for HIV, or Hepatitis B surface antigen (HBsAg)
5. Systemic use in the last two weeks or anticipated use during the study of any of the following: antiretrovirals (e.g. Viread®, Atripla®, Emtriva®, or Complera®), or drugs that may interact with TFV (e.g., protease inhibitors, anticonvulsants, antimycobacterials, St. John's Wort).
6. Participation in any other investigational trial with use of a drug/device within the last 30 days or planned participation in any other investigational trial with use of a drug/device during the study
7. Grade 2 or higher laboratory abnormality, per the 2014 update of the Division of AIDS, National Institute of Allergy and Infectious Disease (DAIDS) Table for Grading the Severity of Adverse Events, or clinically significant laboratory abnormality as determined by the clinician
8. Abnormal finding on laboratory or physical examination or a social or medical condition in the volunteer which, in the opinion of the investigator, would make participation in the study unsafe or would complicate interpretation of data

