7.3.2. Target Enrollment

Participants who initiate product use but discontinue the study prior to completion may not re-enroll. Participants will be screened and enrolled so that approximately 14 women (7 per adherence cohort) complete all study visits.

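### PPV and NPV are to be taken directly from samples whose positive share is set by the visit and dosing plan, so they describe this sample mix and not a clinic

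*Combined protocol and SAP*

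**What the plan says.** The overall objective in Section 5.2 covers all three fluids: "Compare plasma, urine, and vaginal fluid TFV concentrations measured by the aptasensor with those values quantitated by LC-MS/MS". PPV and NPV are named there, and again in the primary plasma objective in 5.2.1 ("to determine agreement between the two methodologies, sensitivity, specificity, NPV, and PPV") and the secondary urine objective in 5.2.2. The bullets on vaginal fluid in 5.2.2 do not name them.

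Section 14.4, repeated in the synopsis, says how they are obtained: "From this comparison, sensitivity, specificity, NPV, and PPV of the aptasensor will also be determined". Confidence intervals are to accompany them. The drug-free samples are the 14 collected at baseline, one from each participant, who thereby acts as control for herself. The section gives their purpose: "these pre-dose samples will be used for the assessment of specificity and NPV".

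Sampling is "at baseline (pre-dose), 24 hours, 7 days and 14 days after dosing" (5.3.1; the same times for urine and vaginal fluid in 5.3.2), with a target that "approximately 14 women (7 per adherence cohort) complete all study visits" (7.3.2).

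The documents state no target prevalence, no conversion of PPV or NPV to another setting, and no limit on how the two are to be read. They give no positivity cut-off for either assay.

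**The concern.** Sensitivity and specificity are each conditional on true status, so the ratio of positive to negative samples does not enter them. PPV and NPV are conditional on the test result, so that ratio does enter. In a clinic it is a feature of the patients. In this trial it follows from how many visits come before and after dosing, and from how long after a dose the samples are drawn.

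The background in the synopsis presents the sensor as a tool for adherence feedback when a prescription is renewed, and says the statistics will guide its further development. A PPV or NPV read as a property of the sensor could mislead that work, and a confidence interval around it would not warn the reader. The interval covers sampling error at this mix of samples, not a change of mix.

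NPV has a second problem. Section 14.4 assigns its assessment to the pre-dose samples. If NPV were computed from those alone, it could not tell a good sensor from a poor one.

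**Working it through.** **Inputs from the documents.** 14 women (7.3.2, 14.4); one pre-dose and three post-dose sampling times (5.3.1, 5.3.2, 8.2, 8.3, Tables 6 and 7); recent antiretroviral use excluded (7.2: "Systemic use in the last two weeks or anticipated use during the study of any of the following: antiretrovirals"), so baseline should be drug-free; LC-MS/MS as reference (5.1). **Assumptions.** Sensitivity (Se), specificity (Sp) and prevalence (p), since the documents give none.

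**Step 1: the plan's own figure.** Pre-dose samples per fluid: 14 × 1 = 14, as 14.4 states. Post-dose: 14 × 3 = 42. Exposed share: 42/56 = 75%. The split between regimens does not change this.

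**Step 2: from exposed to LC-MS/MS-positive.** In the example schedule of Table 7, low-adherence Visits 4 and 5 fall on a Monday after a Friday dose, about 72 hours later. That is 7 × 2 = 14 of the 42 post-dose samples. If 0, 7 or all 14 read negative on LC-MS/MS, the positive share is 42/56 = 75%, 35/56 = 62.5% or 28/56 = 50%. A cut-off high enough to turn other post-dose samples negative would lower it further.

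**Step 3: dependence on the positive share.**

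PPV = Se·p / [Se·p + (1 − Sp)(1 − p)]

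NPV = Sp(1 − p) / [Sp(1 − p) + (1 − Se)p]

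With Se = Sp = 0.90 at p = 0.75: PPV = 0.675/(0.675 + 0.025) = 0.964 and NPV = 0.225/(0.225 + 0.075) = 0.750.

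| Positive share | PPV | NPV |
|---|---|---|
| 30% | 0.794 | 0.955 |
| 50% | 0.900 | 0.900 |
| 62.5% | 0.938 | 0.844 |
| 75% | 0.964 | 0.750 |
| 90% | 0.988 | 0.500 |

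Other assumed sensors behave alike. Se 0.95 with Sp 0.70 gives PPV 0.905 at 75% positive, 0.760 at 50% and 0.576 at 30%. An uninformative sensor (Se = Sp = 0.50) gives PPV 0.75 at 75%, which is simply the share put in.

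**Step 4: effect of the schedule alone.** With one post-dose visit in place of three, the mix would be 14:14. If every post-dose sample is positive, PPV at Se = Sp = 0.90 moves from 0.964 to 0.900 with the same sensor.

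**Step 5: NPV from pre-dose samples alone.** NPV = TN/(TN + FN). If all 14 are truly negative, FN = 0 and NPV = TN/TN = 100% whenever at least one reads negative. A sensor with 1 negative reading in 14 (specificity 7%) and one with 14 in 14 (specificity 100%) both show 100%. The false negatives can come only from truly positive samples.

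**The case against.** The strongest defence is that this is a feasibility-sized, mainly descriptive pilot. No decision rule depends on PPV or NPV, and sensitivity and specificity will be reported beside them. That is true and limits the consequence. It does not answer the point: the caution in 14.4 concerns multiplicity and Type I error, not prevalence, and both measures are written into the primary objective.

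A reader might infer that the schedule fixes a 3:1 ratio of positive to negative samples. The documents do not support that. The 3:1 is a ratio of exposure among completers. PPV is judged against LC-MS/MS, whose results depend on an unstated cut-off and on the late low-adherence samples. Missing samples, which are not imputed (14.2), would also shift the ratio slightly.

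A reader might also infer that the trial's PPV will be too high in practice. That does not follow. The intended users already hold prescriptions, and their positive share is not given; above the trial's share, the counted PPV is too low. The definition of positive matters too. If it meant a post-dose sample on the high-adherence regimen, the share would be 21/56 = 37.5%, with PPV 0.844 at Se = Sp = 0.90, below the 0.900 that applies at 50%.

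Perfect specificity would make PPV 1 at any prevalence, but this trial could not establish it. Even 14 of 14 negatives leaves an exact 95% lower limit of 0.025^(1/14) = 0.768. At that limit with Se = 0.90, PPV is 0.921 at 75% positive and 0.625 at 30%.

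Nor is the planned interval empty: the design influences prevalence, but PPV still varies with the sensor's errors. Finally, the wording on the pre-dose samples may mean only that they supply the true negatives for an NPV counted over all samples. Then Step 5 falls away, but the dependence in Step 3 remains.

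**Conclusion.** The point holds for both PPV and NPV. As planned, they are properties of a sample mix that is 75% exposed and perhaps 50% to 75% LC-MS/MS-positive. Over that range alone, at an assumed Se = Sp = 0.90, PPV runs from 0.900 to 0.964 and NPV from 0.90 down to 0.75. Against a setting with 30% positive, a counted PPV of 0.964 would overstate a true 0.794; against one with 90% positive it would understate 0.988. For specificity below 1, PPV errs upward where positives are less common than in the trial and downward where they are more common. NPV errs the opposite way for sensitivity below 1. The documents do not say which case the intended clinic is.

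The sizes rest on assumed accuracy and prevalence. The dependence itself does not, apart from the extremes of perfect specificity (for PPV) or perfect sensitivity (for NPV). The validity of sensitivity and specificity is not touched by this ratio. NPV from the pre-dose samples alone would carry no information about the sensor if those samples are all truly negative.

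**What to change.** In Section 14.4 and the synopsis:

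- Report sensitivity and specificity against LC-MS/MS, with intervals, as the accuracy measures, at a positivity cut-off fixed before analysis. Without a cut-off none of the four measures can be computed.
- Derive PPV and NPV from them by Bayes' formula over a stated prevalence range, for example 30%, 50%, 75% and 90%, with the uncertainty in sensitivity and specificity carried through to the intervals.
- Use the pre-dose samples for specificity only, not for NPV on their own.
- Label any directly counted PPV or NPV as specific to this trial's sample mix.

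This needs a few sentences and one small table, and no new data. The downside is that PPV and NPV become ranges, less favourable at some prevalences than a single figure would be.
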